NCT number: NCT02936180

**Study title: Improving Influenza Immunization Responses in Rheumatoid Arthritis: A Strategy
To Enhance Protection Against A Preventable Cause Of Death In An At Risk Population?**

Date: 20 November 2019

Statistical Analysis

This study was powered to compare the effect of the HDTIV and SDQIV by background treatment group (stratified analyses), estimating a loss to followup of 10%. Under these assumptions, 92 rheumatoid arthritis patients per strata (46 per vaccine group) were required to assess the primary outcome with a significance level of 5% and 80% power to detect a 30% increase in sero conversion rate for any one common viral strain in the HDTIV group compared with the standard-dose vaccine. This did not include adjustment for multiple testing. Differences of this magnitude have been reported for some strains in immunogenicity studies of HDTIV in older individuals.²⁸

We did a modified intention-to-treat analysis of all outcomes with all randomly assigned participants for whom serostatus was available. The analysis included individuals who did not complete all specified followup visits. We did not do imputations at day 28 as only five patients (<2%) of 279 had missing information for serostatus.

We performed logistic regression and report crude odds ratios (ORs) with 95% CIs to compare the immunogenicity of HDTIV versus the SDQIV for each inactivated influenza vaccine strain. We also calculated ORs (95% CIs) adjusted for age, comorbidities known to reduce immune responses to inactivated influenza vaccines in the general population,⁹ and rheumatoid arthritis disease duration (which predicts the risk of comorbidities).

In a posthoc analysis we performed logistic regression to assess the effect of methotrexate (measured by OR [95% CI]) on responses to HDTIV versus SDQIV. We compared patients on methotrexate (alone or combined with other conventional synthetic DMARDs) versus those on single or combinations of nonmethotrexate conventional synthetic DMARDs, and patients on methotrexate (alone or in combination with other conventional synthetic DMARDs) versus those on biological DMARDs (except rituximab), alone or combined with nonmethotrexate conventional synthetic DMARDs.

A second posthoc analysis using the same method was done to assess the immunogenicity of HDTIV in patients on conventional synthetic DMARDs or targeted synthetic DMARDs versus those on biological DMARDs (excluding rituximab).

Statistical analyses were done with STATA, version 14.2. No data monitoring committee was involved. This trial is registered with ClinicalTrials.gov, number NCT02936180.

Role of the funding source

The funder of the study and Sanofi Pasteur (which provided the vaccines) played no role in study design, data collection, data analysis, data interpretation, or writing of the report. The corresponding author had full access to all the data in the study and with BW had final responsibility for the decision to submit for publication.

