NCT number: NCT02936180

**Study title: Improving Influenza Immunization Responses in Rheumatoid Arthritis: A Strategy
To Enhance Protection Against A Preventable Cause Of Death In An At Risk Population?**

Date 26 August 2016

Executive Summary

Improving influenza immunization responses in rheumatoid arthritis: comparison of standard versus high dose inactivated trivalent influenza vaccine

1. Overview

Four hundred and ten adults diagnosed with seropositive rheumatoid arthritis (RA) will be recruited to a randomized, observer-blind study of standard dose quadrivalent- versus high dose trivalent- inactivated influenza vaccine (SD-QIV vs. HD-TIV respectively) over two consecutive influenza seasons (Year 1: 2016-17/ Year 2: 2017-18). Each year, 205 patients will be stratified according to RA treatment and randomized 1:1 to receive either a single IM dose of a SD-QIV (FLUZONE® Quadrivalent Influenza Vaccine) or a single IM dose of a HD-TIV (FLUZONE® High Dose Influenza Vaccine). Both vaccines are produced by Sanofi Pasteur and are approved by Health Canada for immunization of immunocompromised patients. The primary study outcomes will be the immunogenicity of HD-TIV relative to SD-QIV at 28 days using standard serologic criteria. Secondary and exploratory outcomes will include induction of influenza-specific cellular responses at 28 days, persistence of antibody and cellular responses at 6 months, safety and the frequency of clinical events (i.e. pneumonia and health care utilization) in HD-TIV relative to SD-QIV recipients.

2. Sponsor, Investigator, Study Site

Sponsor

[name]-MBA VP, Research The Arthritis Society Operating Grant	[name], MPH Vice President and Global Medical Expert Sanofi Pasteur Provision of Vaccines
--	--

Nominated Principal Investigator

Co-Principal Investigators

RI-MUHC Vaccine Study Centre (VSC)

[name] RN BScN (Coordinator)
[name]
[name]
[contact]
[contact]
email : [contact] website: www.vaccinestudycentre.com
www.centredeetudedevaccins.com

3. Study Objectives

1) Primary objective

- To determine if the HD-TIV improves immune responses compared to SD-QIV in people with RA using standard serologic criteria based on the hemagglutination inhibition assay (HI) (*Immunogenicity*).

2) Secondary objectives

- To assess the durability of the HI responses after SD-QIV and HD-TIV (*Antibody persistence*).

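### The adjusted odds ratios leave out the randomisation stratum, and no strain or population is named as the answer to the primary objective

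*SAP*

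**What the plan says.** Protocol section 1 (Overview) states that each year "205 patients will be stratified according to RA treatment and randomized 1:1". Section 7 (Study Procedures) defines three strata: DMARDs, anti-TNF, and other biologics or small molecules. Section 3 sets one primary objective: whether the high-dose vaccine improves immune responses in people with RA.

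The SAP (Statistical Analysis) says the trial was powered to compare the vaccines "by background treatment group (stratified analyses". It sizes each stratum at 46 per vaccine group, for a 30% increase in seroconversion "for any one common viral strain in the" high-dose group, and adds: "This did not include adjustment for multiple testing". Crude odds ratios come from logistic regression "for each inactivated influenza vaccine strain". A second set is "adjusted for age, comorbidities known to reduce immune responses to inactivated influenza vaccines in the general population" and for RA disease duration. Treatment stratum is not in that list. The text does not say whether these odds ratios are pooled over strata or fitted within them, or which of them answers the primary objective.

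**The concern.** When randomisation is balanced within strata that differ in response, the two arms resemble each other more closely than under simple randomisation. A pooled model without the stratum ignores this and overstates the standard error. It also estimates an odds ratio averaged over strata, which lies closer to 1 than the odds ratio within each stratum. The plan itself treats background therapy as relevant to response: it stratifies and powers on it, and both post-hoc analyses compare treatment groups. At stake are some precision and a clear meaning for the adjusted odds ratio.

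The second matter is interpretive. One primary question is met by several strain results, in up to three strata or pooled, crude and adjusted, each at 5%. A reader cannot tell which result decides.

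**Working it through.** **1. The plan's own figure.** Inputs from the SAP: 5% level, 80% power, 10% loss, a 30% increase. Assumed: two-sided test, increase in percentage points, control rate 25% (none is given).

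n per arm = [1.96·√(2·p̄(1−p̄)) + 0.8416·√(p₁(1−p₁) + p₂(1−p₂))]² / d²

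With p₁ = 0.25, p₂ = 0.55, p̄ = 0.40, d = 0.30: (1.358 + 0.555)² / 0.09 = 40.7, so 41; 41/0.9 = 45.6, so 46. Control rates of 20 to 50% give 44 to 48. The 46 therefore fits one unadjusted comparison, on one strain, in one stratum.

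**2. Type I error of a pooled analysis without the stratum.** Assumed: three equal strata of 46 per arm, exact balance, no vaccine effect, no other covariates. The variance that applies is proportional to W, the mean of p(1−p) within strata. The unstratified analysis uses p̄(1−p̄). The effective critical value is 1.96·√(p̄(1−p̄)/W).

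| Stratum rates (assumed) | W | p̄(1−p̄) | Effective critical value | Two-sided type I error |
|---|---|---|---|---|
| 20/40/60% | (0.16+0.24+0.24)/3 = 0.2133 | 0.24 | 1.96 × 1.061 = 2.079 | 3.8% |
| 30/40/50% | (0.21+0.24+0.25)/3 = 0.2333 | 0.24 | 1.96 × 1.014 = 1.988 | 4.7% |

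Simulated logistic fits agree: about 3.9 to 4.7% without the stratum and about 5% with it.

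**3. Power at a log odds ratio of 0.7 (odds ratio 2.0) in every stratum.** Take control rates 20/40/60%. The high-dose rates are then 33.5, 57.3 and 75.1%, mean 55.3%, against a control mean of 40%.

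- Without the stratum: log odds ratio = logit(0.553) − logit(0.40) = 0.618, i.e. an odds ratio of 1.86. With 3 × 46 = 138 per arm, SE = √[1/(138×0.40×0.60) + 1/(138×0.553×0.447)] = 0.244, so z = 2.53. The true spread of this statistic is about 0.94, not 1, so power ≈ Φ[(2.53 − 1.96)/0.94] = 73%.
- With the stratum: information = Σ w₀w₁/(w₀+w₁), where w = 46·p(1−p) in each arm, = 4.28 + 5.57 + 4.83 = 14.69. z = 0.7·√14.69 = 2.68, and power ≈ Φ(0.72) = 76%.

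This approximation gives a loss of about 3 to 4 points. Simulation puts it near 5 points at 20/40/60% and near 1 point at 30/40/50%.

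**4. Several strains at 5% each.** Assumed: three common strains (trivalent against quadrivalent), no true difference, equally correlated normal statistics. The documents give no correlation. At correlation 0 the values are 1 − 0.975³ = 7.3% and 1 − 0.95³ = 14.3%; the others come from numerical integration.

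| Correlation | At least one strain favours high dose (one test: 2.5%) | Either direction (one test: 5%) |
|---|---|---|
| 0 | 7.3% | 14.3% |
| 0.5 | 6.3% | 12.5% |
| 0.7 | 5.5% | 10.9% |
| 0.9 | 4.2% | 8.4% |

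With Holm over the three strains, the column favouring high dose becomes 2.5 to 1.5%.

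**The case against.** The strongest reply on the stratum is that the SAP says its comparisons are stratified by background treatment. If every odds ratio was fitted within a stratum, no stratum term is needed. That stands, so the point is conditional on pooling; the SAP should say which was done. A second reply is that the omission cannot produce a false claim. That also stands. A reader might infer that leaving out a design factor inflates type I error, but under balanced stratified randomisation it lowers it. The listed covariates may also recover part of the loss, by an amount the documents do not allow one to estimate.

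On multiplicity, a reader might infer that the trial runs an 8 to 14% chance of false success. The documents do not support that. They write no rule that one significant strain is enough; the sample-size phrase can equally mean power for any given strain. The absence of adjustment is openly disclosed. The objective is also directional, so only results favouring the high-dose vaccine could be false successes, which gives 4 to 7% against 2.5%. Counting all nine strain-by-stratum tests would give 12 to 20% in that direction with independent strata, but this needs a further unwritten rule that any stratum suffices.

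Protocol section 9 does state immunogenicity criteria: lower confidence bounds of 40% for seroconversion and 70% for seroprotection, and a mean fold rise above 2.5. The two rate criteria apply within a vaccine group, the fold rise compares Day 28 with Day 0, and none decides between the vaccines. What remains is that no comparison is named.

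**Conclusion.** The point holds in a limited form. If the per-strain odds ratios are pooled, omitting the stratum makes the comparison conservative (about 3.9 to 4.7% instead of 5%) and costs about 1 to 5 points of power. This rests on equal strata of 46 per arm, the assumed stratum rates and a common log odds ratio of 0.7. If stratum rates hardly differ, the loss is negligible. It is a matter of efficiency and clarity, not of validity.

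Secondarily, 5% holds for each comparison and not for the primary objective as a whole. The 4 to 7% figure illustrates one possible reading of success; it is not a property of a rule the SAP contains.

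**What to change.** State whether each odds ratio is pooled or within stratum. Include the three-level randomisation stratum in every pooled per-strain logistic model, with the crude odds ratios kept beside it. Show the by-stratum odds ratios with evaluable numbers per arm.

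Label the strain results as per-comparison and unadjusted. Holm-adjusted p-values over the common strains may be added, marked as specified late: the SAP is dated November 2019 and already reports that "only five patients (<2%) of 279 had missing information for serostatus". Make no overall superiority claim from a single unadjusted strain.

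The cost is two extra parameters per model, a rerun on existing data and one table. The stratum-adjusted odds ratio is conditional on stratum and need not equal the crude one, so the report should say so. Holm, if used, lowers power for a lone strain: at about 137 per arm pooled ((279 − 5)/2), worst-case power for an assumed 20-point difference falls from about 92% to 83%. A rule chosen with data in hand can limit the claim but cannot restore prespecification.

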- To compare the rates of side effects following SD-QIV and HD-TIV (*Safety*).
- To test for associations between disease and patient characteristics, and vaccine-induced protection for SD-QIV and HD-TIV (*Predictors of response to influenza vaccine in RA*).

3) Exploratory objectives

- To assess the performance of microneutralization (MN) and single radial hemolysis (SRH) assays compared to the HI assay in SD-QIV and HD-TIV recipients with RA (*Serologic readouts*).
- To describe the poly-functional CD4⁺ T-cell response to the SD-QIV and HD-TIV formulations for each strain (*Cellular immune responses*).
- To describe the rates of pneumonia and health care use (hospitalizations, emergency room visits, and other physician contacts) in patients receiving SD-QIV or HD-TIV (*Clinical impact*).

4. Recruitment Process

Pre-recruitment of study candidates will be done by rheumatologists working at the (A) Montreal General Hospital (MUHC), (B) Royal Victoria Hospital (MUHC), and (C) Sir Mortimer B. Davis – Jewish General Hospital prior to the start of the 2016-17 and 2017-18 influenza seasons.

5. Study Period

This study will begin as soon as the SD-QIV and HD-TIV vaccines become available in Quebec for the 2016-17 (Year 1) and 2017-18 (Year2) influenza seasons. Active enrollment each year will continue until December 30th. The duration of each subject's participation in the respective study years will be 186 days.

6. Main Criteria for Inclusion/Exclusion

Adult (>18 years old) females or males with a diagnosis of seropositive (rheumatoid factor (RF) and/or anti-CCP antibody positive) RA treated for at least 6 months with any of the following agents as mono- or combo- therapy: DMARDs (i.e. methotrexate, hydroxychloroquine, sulfasalazine), biologics (i.e. anti-TNF, abatacept, rituximab, tocilizumab) or small molecules (tofacitinib). No major changes of DMARDs or biologics should have occurred in the 30 days prior to enrollment, and no intention to switch therapy within 30 days following vaccination should be present.

Subjects must be accessible by phone or text on a consistent basis and available at day 28.

Subjects who have received vaccination against influenza in the 6 months preceding the trial vaccination or with any of the following conditions will be excluded from enrollment:

- Systemic hypersensitivity to eggs, or any of the vaccine components, or a history of a life-threatening reaction to TIV or to a vaccine containing any of the same substances.

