- 1) Collect patient's diary + medication list and self-assessment of RA disease activity
- 2) Draw a blood samples (as per visit #1) for serology & cellular assays
- 3) Schedule Visit 3 (Day 186 ± 7 days)

Monthly d28-d186 Monthly calls to document pneumonia or non-routine health care use

Day 186 (±7) **Visit 3**

Nurse 1

- 1) Collect medication list and patient-self assessment of RA disease activity
- 2) Draw blood samples (as per visit #1) for serology and cellular assays

8. Safety

Safety and tolerability endpoints will include events recorded in the diaries as well as solicited during visits and telephone calls. These will include both local reactions (eg: erythema, swelling, and pain at the injection site) and systemic symptoms (eg: headache; fever; muscle aches; joint aches; fatigue; chills; malaise; and swelling in the axilla and neck) as well as any other adverse events (AEs). The intensity of the solicited local and systemic reactions will be graded as mild (1), moderate (2), severe (3), or potentially life threatening (4). The causal relationship with the test vaccine will be assessed by one of the principal investigators (PIs) as definitely not related, probably not related, possibly related, probably related, or definitely related. The occurrence of any serious adverse event (SAE) deemed to be possibly-, probably- or definitely-related to the vaccine administered will be assessed by one of the PIs as appropriate (eg: physical examination, vital signs, laboratory investigations, etc). The solicited signs and symptoms will be reported by each subject and recorded from the time of study vaccine administration to 30 minutes (Immediate: Visit #1), between day 1 to d7 days (phone contact) and between d8 and d28 (visit #2). Any new onset of chronic disease (NOCD) reported at any visit or during any telephone contact will be recorded and investigated appropriated by one of the PIs.

9. Immunogenicity Endpoints

Immunogenicity (Primary endpoint): Immunogenicity will be evaluated primarily by measuring the serum HI response against the homologous strains induced in subjects. Serum HI responses will be described in terms of geometric mean titers (GMTs) of HI antibody on Day 0 and Day 28 as per the May 2007 serological criteria for influenza vaccine immunogenicity issued by FDA, namely:

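### The SAP applies one analysis set, participants with serostatus available, to all outcomes, and no safety population is defined

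*SAP*

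**What the plan says.** The analysis population is set out in three consecutive sentences of the SAP, under Statistical Analysis:

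- The modified intention-to-treat approach is an "analysis of all outcomes with all randomly assigned participants for whom serostatus was available".
- On people with missed visits, the next sentence says: "The analysis included individuals who did not complete all specified followup visits".
- Day 28 values were not imputed, because "only five patients (<2%) of 279 had missing information for serostatus".

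No safety, vaccinated or as-treated set appears in either document, and the SAP gives no method for safety or clinical events.

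The protocol, Section 3, has a secondary safety objective, "To compare the rates of side effects following SD-QIV and HD-TIV", and an exploratory clinical objective, "To describe the rates of pneumonia and health care use". Section 8 takes safety data from diaries, visits and telephone calls, in windows of 30 minutes, Days 1 to 7 and Days 8 to 28. Section 7 provides "Monthly calls to document pneumonia or non-routine health care use" from Day 28 to Day 186. At Visit 2 (Day 28), the nurse collects the patient's "diary + medication list and self-assessment of RA disease activity". Blood for serology is drawn at Day 0, Day 28 and the final visit.

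**The concern.** A serology result is a sensible entry condition for comparing seroconversion or seroprotection. It is not a sensible one for side effects, pneumonia or health care use, which are recorded without any blood result. The 30-minute observation and the Day 7 call both come before the Day 28 sample. A vaccinated person could therefore have a recorded reaction, then have no Day 28 result, and fall outside the only set the SAP defines.

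What is at stake is the completeness of the safety denominators and counts. Someone who reacts and withdraws before Day 28 is the kind of participant such a rule could remove. If the rule was never meant to reach safety, a reader still cannot tell who was counted in the side-effect comparison.

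**Working it through.** **The plan's own figure.** 5/279 = 1.79%, which agrees with the stated under 2%. If the five lie outside the set, 279 - 5 = 274 remain.

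**What the text leaves open.**

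| Question | What the documents give | Consequence |
|---|---|---|
| Which visit's serostatus? | Not stated; Day 28 is inferred from the imputation sentence | If Day 0 serostatus suffices, early withdrawals stay in the set |
| What does 279 count? | Not stated; number randomised is the natural reading | If 279 is the analysis set itself, the five were not dropped and the number excluded is unknown |
| Does keeping people with missed visits lift the serostatus condition? | Not stated | Someone can miss the final visit and still have Day 28 serostatus, so the two sentences can both apply |

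**Size, if serostatus means Day 28 and 279 is the number randomised.** The arm sizes are assumed to be 139 and 140 (from 1:1 allocation). The reaction rate r among those analysed, and the arm and reaction status of the five, are also assumptions.

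With k dropped from an arm of n, the rate in the full arm differs from the analysed rate by k(1 - r)/n if all k reacted, and by -kr/n if none did. The standard error (SE) of the between-arm difference is sqrt(r(1 - r)(1/139 + 1/140)).

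| Scenario | r = 30% | r = 50% |
|---|---|---|
| Split 3/2, all reacted: 3(1 - r)/139 - 2(1 - r)/140 | 0.51 points | 0.36 points |
| All five in one arm, all reacted: 5(1 - r)/139 | 2.52 points | 1.80 points |
| All five in one arm, none reacted: 5r/139 (opposite direction) | 1.08 points | 1.80 points |
| SE of the difference | 5.49 points | 5.99 points |
| 95% half-width, 1.96 × SE | 10.8 points | 11.7 points |
| Largest shift / SE | 2.52/5.49 = 0.46 | 1.80/5.99 = 0.30 |

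The ratio rises as reactions become less common. At r = 10%, the extreme case is 5 × 0.9/139 = 3.24 points against an SE of sqrt(0.09 × (1/139 + 1/140)) = 3.59 points, a ratio of 0.90. The statement that the shift is under half a standard error therefore belongs to common reactions, at the rates in the table.

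**Rare serious event.** Suppose an arm's only serious event was in one of five dropped people. The report would show 0/134 (exact 95% CI 0 to 2.7%) instead of 1/139 = 0.7% (0.02% to 3.9%). The intervals overlap, but a zero count and a count of one read differently in a safety table.

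These are upper figures under the two stated conditions, because they assume complete reaction data for all five. The diary is collected at the Day 28 visit, so a person who missed that visit may have only the 30-minute and Day 7 information and any monthly calls.

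**The case against.** The strongest reply is that the set was meant for serology alone. Every method the SAP describes concerns immunogenicity: odds ratios by strain, adjusted odds ratios and two post-hoc analyses of vaccine response. On that view, the reference to all outcomes means all serologic outcomes. This reading is possible, so the documents do not establish that safety was conditioned on a blood result. It does not remove the point, because the population for a stated secondary comparison is then undefined.

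A second reply is that no visit is named for serostatus. Blood is drawn at Day 0 too, listed before the vaccine is given, and the sentence keeping people with missed visits fits a Day 0 reading. This stands as a limit: Day 28 is an inference. Similarly, explaining why the five were not imputed would be largely unnecessary if they were already outside the set, so the figure of 5 of 279 is conditional.

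A third reply is that the effect is negligible. For common reactions this is right.

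A reader might go further and infer that people who reacted to vaccine were removed from the safety comparison. The documents do not support that. They do not say why the five lack serostatus, whether they were vaccinated, whether they had events, or whether they were left out.

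**Conclusion.** The point holds as a defect in the stated rule. As written, the only analysis set ties safety and clinical events to serology they do not need. On the narrower reading, the safety population is missing. Either way the SAP needs the same correction.

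The size rests on two unstated conditions: that serostatus means Day 28, and that 279 is the number randomised with the five outside the set. If both hold, at most 1.8% of participants are affected. That is negligible for common reactions and relevant only where a single event changes the picture. No bias in reported safety results is shown.

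Separately, and as a minor note, Table 1 of the protocol places stratification and randomisation in the column for Day -120 to -1, while Section 7 lists them under Day 0. A reader might infer that patients were randomised before consent, or that an imbalance resulted. The documents do not support either inference: Section 7 is arranged partly by staff role and is not strictly chronological, and no effect on the results is shown.

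**What to change.** In the SAP:

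- Restrict the serostatus-available set to immunogenicity outcomes, and name the visit whose serostatus defines it.
- Analyse side effects and clinical events in all vaccinated participants, using whatever safety data exist.
- Give denominators by arm. Giving them by collection window (30 minutes, Days 1 to 7, Days 8 to 28, monthly calls) would show how much data stand behind each rate.
- State what 279 counts, and report by arm anyone randomised but not vaccinated.

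The cost is two or three sentences, plus a rerun of the safety tables if the five were left out. No extra patients, visits or data are needed. The downside is that safety and immunogenicity denominators will differ slightly, which a footnote can explain.

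For the minor note, one line should reconcile Table 1 with Section 7. Because the SAP is written in the past tense, that line should record when randomisation was actually done relative to consent and the eligibility review.

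### The SAP sizes the trial by treatment stratum but specifies no vaccine comparison within the randomised strata, and its models leave out stratum, season and Day-0 HI titre

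*SAP*

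**What the plan says.** **Sizing.** The SAP's Statistical Analysis section says the trial was powered to compare the vaccines "by background treatment group (stratified analyses"). It states that "92 rheumatoid arthritis patients per strata (46 per vaccine group) were required to assess the primary outcome". The target in each stratum is 80% power at the 5% level for a 30% rise in seroconversion on any one common strain, allowing 10% loss. On multiplicity it says: "This did not include adjustment for multiple testing".

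**Models.** The same section continues: "We performed logistic regression and report crude odds ratios (ORs) with 95% CIs to compare the immunogenicity of" the two vaccines for each strain. A second set of odds ratios is "adjusted for age, comorbidities known to reduce immune responses to inactivated influenza vaccines in the general population", and for disease duration. No other covariate is named, and the text does not say whether these odds ratios are overall, by stratum or both.

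**Post hoc analyses.** The first sets methotrexate users against users of other conventional DMARDs, and also against "those on biological DMARDs (except rituximab), alone or combined with" non-methotrexate conventional agents. The second sets patients on "conventional synthetic DMARDs or targeted synthetic DMARDs versus those on biological DMARDs (excluding rituximab") against each other for HD-TIV response.

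**Design.** Protocol section 7 defines three strata: green (DMARDs), yellow (anti-TNF) and red (other biologics and small molecules). Section 1 stratifies each year's patients by treatment before 1:1 randomisation, over two seasons. Section 9 measures HI titre at Day 0 and Day 28. The primary objective in section 3 is an overall comparison in people with RA and does not mention strata.

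**The concern.** The sample size was chosen so that each treatment group could be read on its own. The analysis text gives no model, estimate or output for that reading. If the benefit of HD-TIV is similar across strata, an overall odds ratio per strain is enough. If it is uneven, the overall figure averages it, and groupings that cut across the strata do not recover the separate effects.

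A smaller matter is efficiency. Stratum, season and Day-0 titre are all available, and each may predict response. Leaving them out of both models may give up precision that would cost nothing to keep.

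**Working it through.** **1. Reproduce the stated size.** Inputs from the SAP: 5% significance (two-sided assumed), 80% power, 30% increase, 10% loss. The control rate is not given, so I varied it from 20% to 50% and read 30% as percentage points. The two-proportion formula with pooled variance is

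n = [1.96√(2p̄(1−p̄)) + 0.8416√(p₁(1−p₁)+p₂(1−p₂))]² / (p₂−p₁)²

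For 25% against 55%, p̄ = 0.40 and n = (1.358 + 0.555)²/0.09 = 40.7, so 41 per arm. Then 41/0.9 = 45.6, so 46, as stated. A control rate of 45% gives the same result, and rates of 20-50% give 44-48. A relative 30% increase would need 772 per arm before loss at a 20% control rate and 55 at 70%. With 46 per arm its power over that range is 10-73%. Percentage points is therefore the natural reading.

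**2. Totals.** 3 × 92 = 276. The SAP reports 279 patients, of whom 279 − 5 = 274 had serostatus. The protocol planned 410, about 137 per stratum if split equally (410/3). The documents do not reconcile 410 with 276.

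**3. Power for different effect patterns.** Assumptions: equal strata of 46 per arm, pooled 274/2 = 137 per arm, control rate 20-50%.

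| Effect in the three strata (points) | Pooled power | Within-stratum power |
|---|---|---|
| 30 / 30 / 30 | over 99% | 83-87% each |
| 30 / 20 / 10 | 92-96% | 83-87 / 48-55 / 16-20% |
| 30 / 15 / 0 | 70-80% | 83-87% in the first |
| 30 / 0 / 0 | 38-48% | 83-87% in the first |

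With 41 evaluable per arm, within-stratum power for 30 points is 79-83%. As an illustration of averaging, take a control rate of 35% and a 30-point benefit in one stratum only. That stratum's odds ratio is (0.65/0.35)/(0.35/0.65) = 3.45. The pooled rates are 45% and 35%, giving 1.52.

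**4. Do the post hoc groups supply the strata?** They do not.
- Targeted synthetic agents (red) are placed with conventional DMARDs (green).
- Anti-TNF (yellow) is merged with other biologics (red).
- Rituximab, which is eligible under protocol section 6, is excluded.
- A patient on a biologic plus methotrexate is on neither side of the second methotrexate contrast.
- The second analysis compares drug groups for HD-TIV response, not HD-TIV with SD-QIV.

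**5. Precision of a by-stratum estimate.** At 46 per arm, 30% against 60%, SE(log OR) = √(1/(46·0.3·0.7) + 1/(46·0.6·0.4)) = 0.441. The 95% interval is the odds ratio divided or multiplied by exp(1.96 × 0.441) = 2.4. Over control rates of 20-50% the factor is 2.4-2.5, and the risk difference is ±19 points. For the contrast of two strata (30 points against none) the SE is 0.61-0.70. Detecting it with 80% power would need a ratio of odds ratios of exp(2.80 × SE) = 5.6-7.2.

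**6. Multiplicity.** Three strata at 5% each: 1 − 0.95³ = 14% per strain. Three strata by three common strains (three assumed from trivalent): 1 − 0.95⁹ = 37% if independent, which is an upper figure. Bonferroni over three strata would cut within-stratum power from 83-87% to 69-74%.

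**7. What the missing covariates might be worth.** This was simulated with 276 patients, three equal strata, two seasons, baseline GMT about 20 with SD 1.5 log2, a vaccine effect of 0.55 log2 and control seroconversion about 35%. All of these are assumptions. Entries are the variance of the standardised risk difference from the crude model, divided by that from a model with vaccine, stratum, season and log2 Day-0 titre. The two values are for residual SD 1.0 and 1.5.

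| Slope of Day-28 on Day-0 titre | Seroconversion | Seroprotection |
|---|---|---|
| 0.2 | 1.18 / 1.08 | 1.04 / 1.02 |
| 0.6 | 1.01 / 1.00 | 1.31 / 1.15 |
| 0.8 | 1.00 / 1.00 | 1.45 / 1.27 |

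With no vaccine effect, rejection was 3.6-5.0% for the crude model and 4.5-5.9% for the fuller one, so neither shows material inflation of type I error.

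**The case against.** The strongest reply is that this is a reporting gap. The sizing sentence names stratified analyses, and the logistic regression paragraph never says pooled or overall, so the by-stratum odds ratios may have been computed. That stands. A reader might infer that the trial analysed the strata only together, but the text is silent and does not show it. What can be said is that no by-stratum model or output is specified.

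Second, the protocol's primary objective is overall, and a pooled odds ratio per strain answers it. That also stands. Stratum-based sizing appears only in the SAP, and the protocol planned 410. A reader might take the closeness of 276 to 279 as proof that by-stratum comparison was always the design. The unreconciled 410 prevents that.

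Third, pooling often does better. Under 30/20/10 it has 92-96% power while the two weaker strata have at most 55%. The within-stratum advantage is large only under 30/0/0, an extreme pattern that nothing in the documents suggests. The case for by-stratum estimates is therefore that the SAP sized for them, not that pooling lacks power.

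Fourth, seroconversion already uses the Day-0 titre in its definition, and the precision gain rests on assumed inputs. Both are true, so the covariate point is secondary. Nor do the omissions make the crude odds ratio biased: allocation is randomised and the crude comparison is valid.

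Fifth, the post hoc analyses are labelled as such and are not offered as the stratified analysis. They are not errors, but they do not fill the gap.

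**Conclusion.** The point holds as a gap in specification with a cheap remedy. The comparison that set the sample size has no stated model or reported quantity, and two sensible uses of collected data (by-stratum estimates and covariate adjustment) are missing from the text. The pooled crude odds ratio remains valid for the overall objective.

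The cost is the by-stratum answer, for which the design has 83-87% power at 46 per arm or 79-83% at 41 evaluable. These figures assume a 30-point effect, a control rate of 20-50% and equal strata, none of which the documents state. There is also some precision, from nothing to a variance ratio of about 1.2 for seroconversion and 1.02-1.45 for seroprotection at the slopes tabulated. Those ranges depend wholly on the assumed titre correlations. By-stratum estimates would be imprecise and could not settle whether the effect differs between strata.

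**What to change.** Keep the crude and adjusted odds ratios as they are. Add the following, labelled as supplementary and specified after data collection or, if already done, state the model used:

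- **(a) By stratum.** For each common strain, give the unadjusted HD-TIV against SD-QIV odds ratio and risk difference, with 95% CI and number per arm, within the green, yellow and red strata as randomised.
- **(b) Overall.** Fit a model for response on vaccine, stratum, season and log2 Day-0 HI titre, with a standardised risk difference. Season applies where a strain's results span both years. Note that the crude odds ratio is marginal and the adjusted one conditional, so the two need not agree.
- **(c) Caveats.** State that by-stratum results are not adjusted for multiplicity (about 14% familywise error per strain; up to about 37% over three strata by three strains), that intervals are wide, and that any vaccine-by-stratum interaction is descriptive only.
- **(d) Sample size.** Say how the protocol's 410 became 92 per stratum, and whether 30% means percentage points and from what control rate.

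The cost is a little analysis and a table or two, with no new patients or samples. The SAP is dated 20 November 2019 and already reports observed missingness, so none of this can be presented as prespecified or replace the stated models.
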